Analysis plan for Aim 2. Our data from Aim 2 will provide estimated effect sizes to inform the sample size of a confirmatory Phase III RCT, per clinical trial guidelines (Freidlin et al., 2012). Our planned sample size is 54 participants total (36 in the POSTHOC group, 18 in the control group); we factor in 15% missing data to yield evaluable data from 46 participants total (31 for POSTHOC, 15 for control). Hypotheses will be tested at $\alpha=0.15$ (2-tailed) as appropriate for Phase I/II studies of this size (Rubinstein et al., 2005).

Aim: Obtain a preliminary estimate of the effect of the POSTHOC app vs. usual care on cumulative patient-reported symptom burden from the MD Anderson Symptom Inventory (MDASI).

Analysis plan: Cumulative severity is the sum of the individual severity levels from the 13 core symptoms from the MD Anderson Symptom Inventory (ranging 0-130). We will use the analysis of covariance (ANCOVA) with cumulative severity at Week 6 as the outcome, study arm (POSTHOC app vs. usual care) as the main independent variable and cumulative symptom severity at Week 0 as a covariate. In case of significant imbalance in other factors between arms (e.g., age), we might include additional covariates in the model. We chose Week 6 as the primary time point because preliminary data from our group shows greater benefits of behavioral interventions at 6 vs. 12 weeks ([name] et al., in preparation). Similar ANCOVA models will evaluate the effects of the POSTHOC app vs. usual care for each outcome at Week 6 and Week 12. To evaluate the longitudinal trajectory of each outcome, we will use repeated measures linear mixed model (LMM) incorporating the specific outcome at all three time points and using a linear contrast to test effects of POSTHOC app vs. usual care. We will use the intent-to-treat principle.

Analyses for Aim 3 and the Exploratory Aims that evaluate symptoms and feelings are analogous to Aim 2, using ANCOVA and LMM to assess the effects of the POSTHOC app vs. usual care control on each outcome. Exploratory analyses will include tests of moderation effects on the POSTHOC app by physical activity adherence, sex, age, etc.

Analysis Plan for Acceptability and Usability: For acceptability, we will estimate the percentage of patients who liked the app (≥ 3 on a scale of 1-5) or would recommend it to other patients at weeks 6 and 12. A 95% CI will span approximately $\pm 15\%$, and in Aim 1. For usability, we will calculate simple summary statistics for the quantitative measures. We will review the qualitative data to look for general themes related to specific design features that make the app challenging to use or understand.

Assessing whether any observed differences are clinically meaningful:

There are two methods to define the minimal clinically important difference (MCID)—anchor-based or distribution-based (Fleishmann et al., 2019). It is recommended that are both used when available. The MD Anderson Symptom Inventory (MDASI) has not been validated for an anchor-based threshold for MCID. Therefore, we are relying on distribution-based MCID interpretations. For health-related quality of life measures such as what we are measuring herein, a difference of one-half standard deviation tends to provide consistent discernable differences among patients and correlates strongly with anchor-based methods (Norman et al., 2003). This corresponds to an effect size of 0.5 by definition.

We are not powered to test the effect of the app on any of these outcomes, though we will compare our results to that of published literature:

- For the Global Physical Activity Questionnaire (GPAQ) and step counts, a clinically meaningful increase in steps is 800 steps per day or 15% more for an individual, or half-a-standard deviation more for groups (Kalb et al., 2020).
- For the Insomnia Severity Index, there is a validated anchor-based MCID of 6 points (Yang et al., 2009).
- There is no MCID for the dietary assessment. We will look at whether dietary patterns meet guidelines outlined in the Survivorship Care Plan.

Data handling, rigor, quality, and reproducibility. We will capture patient-reported data electronically using the POSTHOC app or REDCap, and, only if necessary, paper-based forms that will be manually entered into REDCap. We will audit our database and visually inspect all data (e.g., Q-Q plots, box-plots, scatter plots). These inspections will include histograms of various explanatory variables as well as plots of means and fitted regression curves. If distributional assumptions are not met (e.g., normality of residuals), we will use transformations or nonparametric methods. We will assess outliers to determine if they are erroneous. If they are valid, we will conduct sensitivity analyses (with and without outliers). We will use SAS, Stata, JMP, and R for the analyses.

Missing data. We will facilitate completion of all measures. The reasons for missing data will be tabulated according to treatment group and magnitude of missing data will be assessed to select appropriate statistical method (e.g., maximum likelihood weighting, multiple imputations).

Sharing of Results

- 1 * Describe whether results (study results or individual subject results, such as results of investigational diagnostic tests, genetic tests, or incidental findings) will be shared with subjects or others (e.g., the subject's primary care physicians) and if so, describe how it will be shared:

As the overall results of this investigation will not affect the participant's treatment, it will not be necessary to discuss the investigation results with participants or their clinical care team. However, data collected from the Fitbit and Dietary Recalls will be available to the participants at the end of the study upon request.

We will post the final results on clinicaltrials.gov at the completion of the study and share de-identified results as part of abstracts and manuscripts.

The POSTHOC app will not be connected to the electronic medical record.

ID: VIEW4E02808CBD800
Name: v2_Sharing of Results

Psychological/Behavioral/Educational Methods & Procedures

You indicated on the "Type of Research" page that your study involves a psychological/behavioral/educational method or procedure such as a survey, questionnaire, interview, or focus group.

- 1 * Select all behavioral methods and procedures which apply to this study:

- Surveys/questionnaires**
- Key informant or semi-structured individual interviews**
- Focus groups or semi-structured group discussions
- Audio or video recording/photographing**
- Educational tests or normal educational practices (education instructional strategies, techniques, curricula, or classroom management methods)
- Individual or group behavioral observations
- Psychosocial or behavioral interventions**
- Neuropsychological or psychophysiological testing
- Deception
- Other psychosocial or behavioral procedures**

ID: V1EW4E09416F57800

Name: v2_Psychological/Behavioral/Educational Methods and Procedures

Surveys/Questionnaires

You indicated that this study involves surveys and/or questionnaires.

If you uploaded a separate research protocol document in the 'Research Protocol' page, cite the applicable section and page numbers from that document in the answer boxes below.

- 1 * List all questionnaires/surveys to be used in the study, including both standardized and non-standardized assessments:
 - On Study
 - MD Anderson Symptom Inventory (MDASI)
 - Functional Assessment of Chronic Illness Therapy-Fatigue (FACIT-F)
 - Brief Fatigue Inventory (BFI)
 - Pain Questionnaire: Brief Pain Inventory-Short Form (BPI-SF) and Pain Catastrophizing Scale (PCS)
 - Insomnia Severity Index (ISI)
 - Global Physical Activity Questionnaire (GPAQ)
 - Chemotherapy-Induced Peripheral Neuropathy (CIPN-20)
 - Distress Thermometer (DT)
 - Healthcare Utilization
 - Acceptability Survey
 - System Usability Scale (SUS)
 - Healthcare Climate Questionnaire (HCCQ) - modified
 - ASA24 Dietary Assessment Tool
 - Ecological Momentary Assessment (EMA) symptom questions

The Daily Nutrition Questions are questions that will come through the app for those in the intervention group who choose to emphasize nutrition.

- 2 * Upload a copy of all questionnaires/surveys:

Name	Created	Modified Date
2023.02.09-EMA.docx(0.03)	10/20/2022 3:25 PM	2/13/2023 10:22 AM
MD Anderson Symptom Inventory (MDASI)(0.02)	9/6/2022 3:47 PM	1/10/2023 10:08 AM
Chemotherapy-Induced Peripheral Neuropathy (CIPN-20)(0.02)	9/6/2022 3:48 PM	1/10/2023 9:23 AM
Daily-Nutrition-Questions_Questions that will come through the app.docx(0.01)	12/16/2022 2:39 PM	12/16/2022 2:39 PM
On Study(0.02)	9/1/2022 10:40 AM	10/21/2022 1:09 PM
Pain-BPI-PCS.pdf(0.01)	10/20/2022 3:47 PM	10/20/2022 3:47 PM
Distress Thermometer (DT)(0.01)	9/6/2022 3:50 PM	9/6/2022 3:50 PM
Global Physical Activity Questionnaire(0.01)	9/6/2022 3:44 PM	9/6/2022 3:44 PM
ASA24 Dietary Assessment Tool(0.01)	9/1/2022 10:11 AM	9/1/2022 10:11 AM
Insomnia Severity Index (ISI)(0.01)	8/31/2022 3:45 PM	8/31/2022 3:45 PM
Brief Fatigue Inventory (BFI)(0.01)	8/31/2022 3:44 PM	8/31/2022 3:44 PM
Functional Assessment of Chronic Illness Therapy-Fatigue (FACIT-F)(0.01)	8/31/2022 3:40 PM	8/31/2022 3:40 PM
System Usability Scale (SUS)(0.01)	8/31/2022 3:26 PM	8/31/2022 3:26 PM
Acceptability Survey(0.01)	8/31/2022 3:21 PM	8/31/2022 3:21 PM
Healthcare Utilization(0.01)	8/31/2022 3:21 PM	8/31/2022 3:21 PM

- 3 * What is the total length of time that each survey is expected to take?

On Study 3-5 min

MD Anderson Symptom Inventory (MDASI) 2-4 min

Functional Assessment of Chronic Illness Therapy-Fatigue (FACIT-F) 4-6 min

Brief Fatigue Inventory (BFI) 2-4 min

Pain Questionnaire 4-8 min

Insomnia Severity Index (ISI) 2-4 min

Global Physical Activity Questionnaire (GPAQ) 2-8 min

Chemotherapy-Induced Peripheral Neuropathy (CIPN-20) 4-6 min

Distress Thermometer (DT) 1 min

Healthcare Climate Questionnaire (HCCQ) 1-3 min

Acceptability Survey 1-2 min

System Usability Scale 4-6 min

Questionnaire packet: 30-50 min

Healthcare utilization: Administered orally and not part of the questionnaire packet: 3-10 min

ASA24® Dietary Assessment Tool: Administered by a trained nutritionist via telephone or video conference: 30-45 min

Automated Self-Administered 24-Hour (ASA24) Dietary Assessment Tool: Administered orally and not part of the questionnaire packet: 30-45 min

See "Other Attachments" for the Data Collection Table

- 4 * Are any of the questions likely to cause discomfort in participants or cause harm if their confidentiality were breached? (i.e., Illegal activities)

Yes No

- 5 * Do any questions elicit information related to the potential for harm to self or others?

Yes No

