If you uploaded a separate research protocol document in the 'Research Protocol' page, cite the applicable section and page numbers from that document in the answer boxes below.

1 * Describe the purpose, specific aims, or objectives of this research. State the hypothesis to be tested:

This is a phase I/II feasibility/preliminary efficacy randomized controlled trial in 54 patients with cancer who recently completed adjuvant treatment for cancer (e.g., chemotherapy, radiotherapy, surgery) to compare 12 weeks of the POSTHOC app as part of the Survivorship Care Plan vs. the usual care Survivorship Care Plan on total symptom burden.

Aim 1: To assess how many participants view or log data in the app at least 3 times per week over the 12-week study. We hypothesize that at least 75% of participants ($\geq 27/36$) will view or log data in the app at least 3 times per week.

Aim 2: To obtain a preliminary estimate of the effect of the POSTHOC app vs. usual care on cumulative patient-reported symptom burden. We hypothesize that the POSTHOC app will reduce cumulative symptom burden reported by patients compared to usual care, as measured by the sum of severities of the core patient-reported symptoms from the MD Anderson Symptom Inventory, including fatigue, insomnia, pain, appetite loss, dyspnea (shortness of breath), cognitive problems, nausea, distress, and sensory neuropathy.

Aim 3: To obtain a preliminary estimate of the effect of the POSTHOC app vs. usual care on patient-reported and objectively measured health behaviors (physical activity, diet, sleep). We hypothesize that the POSTHOC app will improve health behaviors compared to usual care, as measured by patient-reported physical activity (Global Physical Activity Questionnaire) and sleep (Insomnia Severity Index), as well as objective measurements of physical activity (e.g., daily steps) and sleep (e.g., sleep quality) from the activity tracker and diet (i.e., telephone-administered dietary assessment).

Exploratory aims: To assess the acceptability and usability of the POSTHOC app by participants in the POSTHOC intervention group at week 6 and week 12 using questionnaires.

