During the initial meeting with the patient, we will have a member of the study staff explain the purpose of the study and then, if the person is interested in joining the study, obtain their consent for participation. The initial meeting will occur in person, via telephone, or video conference, depending on participant preference. After consent all participants will receive a paper-based Survivorship Care Plan via MyPortfolio. We will administer questionnaires including an On Study form that includes demographics and clinical characteristics and baseline assessments (approximately 35-50 minutes). Questionnaires will be administered via REDCap unless the participant would prefer paper-based questionnaires through the mail. Questionnaires can be completed on any device that has internet, including their computer, tablet, or smartphone, and do not need to be completed in a single sitting; they can be completed on the participants' own time. Participants will receive a Fitbit smartwatch activity tracker and orientation to use of the tracker. Participants will wear the activity tracker for 7 days to assess physical activity and sleep. We will also conduct ecological momentary assessment (EMA) via the activity tracker and POSTHOC app for these 7 days during which participants will be prompted (via notification) to answer 5 questions per day—the default times will be 9am, 12:30pm, 4pm, and 7:30pm but can be adjusted based on the participant's schedule and preferences (ideally begin 1-2 hours after waking). These questions will capture key symptoms—distress, fatigue, pain, numbness/tingling, and interference of any symptoms with daily activity on a scale from 0-10. Dietary intake data will be collected via telephone or video conference by a study team member using the 24-hour (ASA24) Dietary Assessment Tool at baseline, week 6, and week 12.

During the baseline week, all participants will have a "light" version of the POSTHOC app that only has these initial data collection features (e.g., activity tracking, EMA data collection) during the baseline week.

After baseline data collection, participants will be randomized. Randomization will occur 2:1 for POSTHOC app (N=36) vs. control (N=18). We will use a computer-generated table with random blocks of 3 and 6. We will stratify by whether the participant had chemotherapy or not (yes/no).

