Intervention (POSTHOC) group: For participants randomized to the POSTHOC group, the intervention consists of the POSTHOC app, which stores an electronic version of the participant's Survivorship Care Plan and has other useful features available to the participant. Specifically, it will list the names and roles of providers, including an oncologist, primary care providers, and any specialists. It will list upcoming appointments and recommendations for future appointments with the target time frames (e.g., annual mammogram for breast cancer, annual CT scan for colorectal cancer). The Survivorship Care Plan always includes healthy lifestyle behavior goals for nutrition (e.g., losing weight or maintaining a healthy weight), exercise (150 minutes per week or 75 minutes of moderate-vigorous physical activity per week), sleep hygiene, and quitting tobacco products. Upon randomization, the coordinator will ensure that the Survivorship Care Plan is properly entered into the app. The participant will choose whether they want to prioritize nutrition or exercise as part of the study. The coordinator will ensure that the participant understands how to read and interpret either the exercise data or food log data in the app in relation to the goals outlined in their Survivorship Care Plan. The participants in the POSTHOC group who choose to focus on exercise will be encouraged to use their activity tracker for the duration of the 12-week intervention period. The POSTHOC app will pull data from the Fitbit app once both apps are installed and set up, so the participant will not need to enter any activity data manually. Survivorship Care Plans tend to recommend 150 minutes per week or 75 minutes of moderate-vigorous physical activity per week or physical activity. We will not provide the exercise group with any materials or specific exercise regimens. We will listen to what their current activity habits are and how they think they would enjoy increasing their activity to reach the goal. Walking 25 minutes per day will achieve the 150 minutes per week goal, and that will be our first recommendation (e.g., outside, at the mall/Walmart/Home Depot, etc.). Participants who choose to focus on nutrition will be encouraged to answer six brief questions at the end of each day regarding their intake of fruits, vegetables, whole grains, and sweets to daily compare their eating habits to their goals. They will meet a member of the study team to brainstorm how to change their current diet to reach the goals. Participants in the POSTHOC+nutrition group will be told that they do not need to wear the activity tracker except for weeks 6 and 12.

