13. System Usability Scale (SUS) (6 weeks and post-intervention interview only): The System Usability Scale (SUS) is a simple questionnaire giving a global view of subjective assessments of usability. It offers a quick and simple to use questionnaire designed to assess the usability of a particular device or product. The SUS consists of ten usability statements that are rated on a Likert scale of 1 (strongly agree with statement) to 5 (strongly disagree with statement). Answers are coded and a total usability score is derived for the product or device under analysis. The questionnaire also includes an optional free-response comments area.

The self-administered questionnaires that will be completed at Week 0, Week 6, and Week 12 should take approximately 35-50 min in total to complete.

Dietary intake

Dietary intake will be assessed once at baseline, week 6, and week 12. It could occur at the same time as the biweekly check-in or another day that week. The ASA24® Dietary Assessment Tool is a freely available web-based tool used for epidemiologic, interventional, behavioral, or clinical research that enables multiple automatically coded 24-hour dietary recalls. It will be administered by a trained nutritionist via telephone or video conference and takes approximately 30-45 minutes.

Exit interview

After completion of the study (or earlier if a participant withdraws early from the study), a member of the study team will conduct an exit interview to understand the participants' experience of being in the study. We will ask them what they liked about the study, did not like about it, what features they liked/did not like about the POSTHOC app (for those in the intervention arm), if they would recommend the study to others, etc. This interview will be audio-recorded with explicit permission at the time of the interview, then transcribed for qualitative and mixed methods data analysis.

2. * Describe all procedures already being performed for diagnostic or treatment purposes (if not applicable to the study, enter "N/A"):

N/A
3. * Describe the duration of an individual participant's participation in the study:

Participants will participate in the study for approximately 14 weeks, including consent, baseline assessments, a 12-week intervention, and an exit interview.
4. * Describe the amount of time it will take to complete the entire study:

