Usual care arm: The usual care arm will not be encouraged or discouraged from making changes to their daily routines or lifestyle behaviors. We will emphasize the importance of their participation because we do not know a lot about the relationships between healthy lifestyle behaviors (e.g., nutrition, physical activity, sleep) and symptoms in early survivorship.

ID: VIEW4E0BC12A9F800
Name: v2_Behavioral Interventions

Other Psychosocial or Behavioral Procedures

You indicated that this study involves other psychosocial or behavioral procedures.

1 * Describe the other psychosocial or behavioral procedures that will be involved in the research:

Physical activity and sleep will be measured via an activity tracker, a dietary recall will be administered by a study team member, and ecological momentary assessment will be assessed via the POSTHOC app.

Activity tracker: The participants will be asked to wear a Fitbit activity tracker for 7 days during week 0 (baseline), week 6, and week 12. The activity tracker will provide data on physical activity and sleep parameters.

This will not cost the participant any time, other than to charge it every few days.

Very low potential for causing discomfort from the activity tracker (more like annoyance once in a while).

24-Hour Dietary Recall: A member of the study team will perform a 24-hour dietary recall using the standardized 5-pass method and ASA24® Dietary Assessment tool. This is a free, online tool developed by the National Cancer Institute (NCI). The participant will not be told that we will be performing a dietary recall. The interviewer will lead the participant to report everything they have eaten and drunk in the last 24 hours including dietary supplements. The interviewer will specifically probe for add-ins (e.g., sugar to coffee, snacks, and beverages).

Duration: Approximately 30-45 minutes.

Not likely to cause harm.

Ecological Momentary Assessment (EMA): At four time points every day for seven days (at baseline, week 6, and week 12), we will ping the participant to report the severity of 4 common symptoms—distress, fatigue, pain, numbness/tingling, and interference of any symptoms with daily activity on a scale from 0-10. While research studies have shown success with this type of data collection (Kampshoff et al., 2019), participants will have the option to “turn off notifications” if it is too burdensome.

Duration: 30 seconds four times per day for 7 days at baseline, week 6, and week 12.

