- Cancer survivors 18 years and older who finished chemotherapy, radiation, and/or surgery within the last 12 weeks
- People who are experiencing some lingering side effects or symptoms from their cancer or cancer treatment
- People who have access to an Android or Apple smartphone and reliable Internet access

What do I have to do?

- Participate in a 12-week study that collects data on food intake, physical activity, sleep patterns, and common cancer-related symptoms such as distress, fatigue, pain, and numbness/tingling
- Provide feedback on a new smartphone app that monitors your symptoms for one week at the beginning, middle, and end of the study
- Wear a Fitbit smartwatch (that we provide) that monitors activity and sleep patterns for one week at the beginning, middle, and end of the study
- Meet with a nutritionist for 30 minutes at 3 time points to answer questions about your diet (the meeting can take place in-person, via phone or videoconference, your choice)
- Fill out questionnaires related to your eating patterns, fatigue, and other symptoms at the beginning, middle, and end of the study

Do I get paid to participate?

Yes, up to \$50. You also get to keep the Fitbit once all study requirements have been completed.

Can I participate remotely?

Yes, all research activities can be done at home.

Interested?

Contact the study chair, [name], at [contact]

Twitter post:

POSTHOC: Leveraging technology to address post-treatment outcomes of cancer survivors: A clinical trial

The Survivorship Care Plan helps you transition from being on active cancer treatment to long-term post-treatment survivorship and promotes healthy diet and exercise behaviors. We are testing a paper-based vs. digital Plan. Get \$50 and a free Fitbit smartwatch.

Contact [contact]

1.3 * Upload advertisement(s) here:

Name

- Elm Weekly Page WriteUp.docx(0.03)
- Twitter post(0.04)
- Study-Advertisement_Brochure(0.02)
- ResearchMatch_Contact-Message.docx(0.01)
- ResearchMatch_Welcome-Message_For people who have indicated interest in our study via the RM Contact message.docx(0.01)
- Elm-Weekly-Newsletter-Blurb.docx(0.01)

	Created	Modified Date
	12/16/2022 2:09 PM	2/14/2023 2:25 PM
	8/26/2022 7:38 PM	2/14/2023 2:25 PM
	8/19/2022 12:07 PM	2/13/2023 10:33 AM
	12/16/2022 2:09 PM	12/16/2022 2:09 PM
	12/16/2022 2:09 PM	12/16/2022 2:09 PM
	12/16/2022 2:09 PM	12/16/2022 2:09 PM

Research Related Risks

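### The Aim 3 diet measure is a self-report that staff who also coach the POSTHOC nutrition choosers may collect; separate the two roles and label diet as self-reported

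*Combined protocol and SAP*

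**What the plan says.** All references are to the combined protocol and SAP.

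- **Label.** Aim 3 (Justification, Objective, & Research Design, item 1) contrasts patient-reported measures with "objective measurements of physical activity (e.g., daily steps) and sleep (e.g., sleep quality) from the activity tracker and diet (i.e., telephone-administered dietary assessment").
- **Measure.** Study Procedures, item 1: "Dietary intake data will be collected via telephone or video conference by a study team member using the 24-hour (ASA24) Dietary Assessment Tool". The Dietary intake paragraph adds "Dietary intake will be assessed once at baseline, week 6, and week 12". Other Psychosocial or Behavioral Procedures, item 1, describes an interviewer who leads the participant through everything eaten and drunk in the past 24 hours, by a standardized 5-pass method.
- **Interviewer.** A study team member in two places; a trained nutritionist in the Dietary intake paragraph and in Surveys/Questionnaires, item 3.
- **Timing.** Of the recall: "It could occur at the same time as the biweekly check-in or another day that week". The check-in call serves to encourage engagement, monitor adverse events and gather app feedback.
- **Coaching.** POSTHOC participants who choose nutrition are encouraged to answer six daily questions on fruits, vegetables, whole grains and sweets. In addition, "They will meet a member of the study team to brainstorm how to change their current diet to reach the goals".
- **Blinding.** The research design item says that neither the PI nor the coordinators are blinded and that participants cannot be.
- **Advance notice.** Other Psychosocial or Behavioral Procedures: "The participant will not be told that we will be performing a dietary recall". The brochure under Advertising Detail: "Meet with a nutritionist for 30 minutes at 3 time points to answer questions about your diet".
- **Analysis.** Sample Size and Data Analysis, item 2, gives Aim 3 outcomes an ANCOVA and a mixed model between arms. It states that no MCID exists for diet, and adds: "We will look at whether dietary patterns meet guidelines outlined in the Survivorship Care Plan".

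**The concern.** A 24-hour recall depends on what the participant chooses to report and on how the interviewer probes. In an open-label trial, a participant who has set diet goals with a staff member, and who logs the same foods daily, has a reason to report eating them. That reason is stronger if the person asking helped to set the goals or asks during a call meant to encourage engagement. Usual-care participants have less of it. The difference arises after randomization, so neither randomization nor adjustment for the baseline recall removes it.

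The label matters as well. A reader who sees diet listed with step counts and tracker sleep data will not discount it as a self-report. The protocol intends these data to inform a follow-on trial, so a shifted diet estimate presented as objective would carry forward.

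**Working it through.** **No diet figure to reproduce.** The documents give no SD, effect size, sample size or power for diet. The check is mainly a reading of the passages against each other.

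| Question | What the text establishes |
|---|---|
| Is diet objective? | No. It is an interviewer-led recall, worded with objective measures in Aim 3. |
| How many recalls? | One per time point, three in all. |
| Is the interviewer blinded? | The PI and coordinators are not. For the nutritionist nothing is stated, and no blinded assessor is described. |
| Are coach and interviewer separate? | No rule says so; both are described as members of the study team. |
| Is the recall separate from the check-in? | Not required. |
| What do the arms receive on diet? | Both have a care plan with nutrition goals. Only POSTHOC nutrition choosers get diet planning and the daily food questions. |

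The baseline recall precedes randomization and cannot differ by arm for this reason. The exposure is at weeks 6 and 12.

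**Illustration of what a reporting shift would do.** From the plan: 31 and 15 evaluable participants, two-sided alpha 0.15, ANCOVA. Assumed: no true diet effect, baseline-to-follow-up correlation 0.5 for diet, and a reporting shift *b* in SD units.

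- Standard error = sqrt(1 − 0.5²) × sqrt(1/31 + 1/15) = 0.866 × 0.3145 = 0.272 SD.
- Whole arm shifts by 0.3 SD: noncentrality 0.3/0.272 = 1.10.
- Half the arm shifts by 0.3 SD: mean shift 0.15 SD, noncentrality 0.15/0.272 = 0.55.

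Chance of a nominally significant result (noncentral t, 43 df), against 15% with no shift:

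| Assumed shift *b* | Half the POSTHOC arm | Whole POSTHOC arm |
|---|---|---|
| 0.2 SD | 18% | 25% |
| 0.3 SD | 21% | 37% |
| 0.5 SD | 31% | 65% |

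With correlations from 0.3 to 0.65, the 0.3 SD row runs from 20% to 23% for half the arm and from 33% to 43% for the whole arm. Only nutrition choosers are coached on diet, so the half-arm column is nearer the mechanism described. The share who will choose nutrition is not given.

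**One recall and individual guideline attainment.** Let R be the assumed ratio of day-to-day to between-person variance. The reliability of one recall is 1/(1 + R), and the share of people misclassified at a guideline set at the median is arccos(sqrt(reliability))/π.

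- R = 1: reliability 0.50, misclassified 25%.
- R = 2: reliability 0.33, misclassified 30%.
- R = 3: reliability 0.25, misclassified 33%.

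This is random error in both arms. It argues against judging individuals on one recall; it does not bias a comparison of arm means.

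**The case against.** Several stronger readings are tempting, and the documents do not support them.

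- **That the bias falls on one arm only.** All participants receive a care plan, which always includes nutrition goals. The coordinator goes through it with each control, and both arms get the biweekly calls. POSTHOC participants who choose exercise get no diet coaching. Greater pressure in part of one arm is the most that can be said.
- **That coach and interviewer are the same unblinded person.** The text permits this but does not state it. The study team member and the trained nutritionist may be one person described two ways.
- **That the brochure cancels the unannounced recall.** The brochure says that diet will be discussed three times; it does not give the day. The other statement can be read as withholding only the day. The two need reconciling, but the safeguard is not shown to be void.
- **That diet will be judged by guideline attainment.** The between-arm ANCOVA is already planned. The guideline sentence sits under clinical meaningfulness and sets no per-person cut-off. A reader might also infer that one recall inflates the share meeting a guideline, but that depends on where the cut-off lies: with symmetric error there is no distortion at the mean, and the sign reverses below it.

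The strongest general defence is that Aim 3 seeks a preliminary estimate, the trial is declared open-label, and the plan says that it is not powered for these outcomes. That stands and limits the weight of the point. The standardized 5-pass method also helps, but it does not stop participants who know their arm from reporting differently.

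**Conclusion.** The point holds in a limited form. Diet in Aim 3 is self-reported and should not be worded with the objective measures. The plan leaves open that unblinded staff who plan diet change with POSTHOC nutrition choosers also take their recalls, possibly during the engagement call. Differential reporting in favour of the app is therefore plausible in part of that arm. Its size cannot be derived from the documents; the false-positive figures rest wholly on assumed shifts and correlations and show only that a modest shift would matter at alpha 0.15. Nothing here shows that an observed diet effect would be an artefact, and the primary symptom outcome is not touched. The changes are worth making because they cost little.

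**What to change.** 1. Have the trained nutritionist already named take all week 6 and week 12 recalls, not told the arm and with no part in coaching or check-ins. Cost: reassignment within existing staff. Recall and check-in can no longer share a call, and some participants will reveal their arm.
2. In Aim 3, describe diet as self-reported by interviewer-led 24-hour recall. Cost: wording.
3. Base the diet conclusion on the between-arm ANCOVA already planned, and name its variables: mean intake of the food groups the app targets (fruits, vegetables, whole grains, sweets). Use care-plan guidelines as group-level description only, not as individual attainment from one recall. Cost: a few sentences.
4. Reconcile the statement that participants are not told of the recall with the brochure's three announced diet meetings, and say whether only the day is withheld. Keep this compatible with the commitment under Privacy of Participants to hold calls by appointment.
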